#### 3.5.1 Power Estimation

For the primary endpoint of the study, there is 83% power to detect a clinically meaningful effect size of 5 units in PROMIS score between control and either VR arms at the 0.05 level of significance. This requires 360 patients randomized on a 1:1:1 ratio.

For one of the secondary endpoints of comparison between the two VR arms, we test the null hypothesis that  $H_0: mv1 = mv2$  versus the alternative hypothesis that  $H_1: mv1 \neq mv2$  at the two-sided 0.05 level of significance if there is statistical evidence that both VR arms are better than control. Using the same assumptions as above and simulating 10000 trial replicates, then if both VR arms are better than the control arm, we can achieve 71.4% power to detect 5 units in PROMIS score between the two VR arms. This power was derived under the alternative hypothesis  $|mc - mv1| = 5$  and  $|mv1 - mv2| = 5$ . The actual type I error rate for this conditional test is 0.02.

For assessing the effect of VR on treatment response, we estimate power using a logistic regression model, accounting for all possible confounding factors as described in the protocol.

The outcome variable is treatment response (binary) and the predictor of interest is VR type, Distraction versus Skills-based. Table 1 gives the minimum odds ratio that can be detected with 80% power with the two-sided 0.05 level of significance as a function of baseline probability of positive response when a patient is treated with traditional VR and  $R^2$ , the proportion of variability in the predictor of interest (VR type) that is explained by all relevant baseline covariates in the model using data from 120 patients in the Distraction VR arm and 120 in the Skill-based VR arm. For example, data from 240 patients achieve 80% power to detect an odds ratio of 2.19 if the probability of positive response when a patient is treated with Distraction VR is 0.3 and 10% of the variability in VR type is explained by all other baseline covariates in the model. These odds ratios vary between 2.01 and 2.8 and are clinically meaningful. Therefore, we have enough power to test statistical significance of predictors of interest in the multivariable logistic regression model.

**Table 1.** Minimum detectable odds ratio as a function of the proportion of variability in VR type variable that is explained by all other relevant covariates in the model and the baseline probability of positive treatment response.

Baseline probability	$R^2$			
	0.0	0.1	0.2	0.4
0.2	2.26	2.36	2.48	2.82
0.3	2.11	2.19	2.30	2.61
0.5	2.01	2.18	2.30	2.64

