### 4.2 SCIENTIFIC RATIONALE FOR STUDY DESIGN

The three-arm study design will allow us to determine whether a skills-based VR program that teaches exportable skills using CBT, guided meditation, and biofeedback-based breathing exercises outperforms conventional, distraction-based VR therapy in reducing cLBP. The 90-day study duration was chosen to assess whether VR therapy's efficacy extends beyond short-term analgesia and reduces the frequency and intensity of ongoing LBP through continuous use over a longer period. It also will enable us to evaluate longer-term change in other PROs and whether continued use of VR reduces opioid use. The

active control group (Sham VR) was designed to minimize bias related to the novelty of the hardware, addressing one of the deficits of prior studies.

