## 9.2 SAMPLE SIZE DETERMINATION

### Sample Size calculations

The primary goal of this aim is to test the efficacy of immersive VR in improving perceived pain. The trial will be a success if there is statistical evidence that either immersive VR group is better than control or sham VR. Preliminary studies showed that the PROMIS pain interference scale has a SD of 10. Assuming that the SD at baseline ( $SD_0$ ) and at 30 days ( $SD_1$ ) are similar and equal to 10 for this population, the variance for the difference in PROMIS from baseline to 30 days after intervention is  $Var_{diff} = SD_0^2 + SD_1^2 - 2\rho SD_0 SD_1$ , where  $\rho$  is the correlation coefficient between measurements at baseline and 30 days. A conservative estimate of this variance is achieved when  $\rho = 0$ . Therefore, the estimate  $SD_{diff} = (10^2 + 10^2)^{0.5} = 14.14$ . Let  $m_c$ ,  $mv_1$ , and  $mv_2$  be the mean change in PROMIS score from baseline to 30 days for the control, VR1, and VR2 groups, respectively.

We estimate power by simulating 10000 trial replicates and testing the null hypothesis that  $H_0: m_c = mv_1 = mv_2$  versus the alternative hypothesis that  $H_1: m_c \neq mv_1$  or  $m_c \neq mv_2$ . To maintain the familywise error rate at 0.05, a two-sample t-test is used to compare the control arm to each VR arm and the test is declared statistically significant if the p-value of the two-sided test is less than 0.025. Under the alternative hypothesis that  $|m_c - mv_1| = |m_c - mv_2| = 5$ , data from 120 patients in each of the three arms achieve 83% power to detect a clinically meaningful effect 5 units in the PROMIS score. The actual type I error rate is 0.049. For the secondary outcome of comparison between the two VR arms, we test the null hypothesis that  $H_0: mv_1 = mv_2$  versus the alternative hypothesis that  $H_1: mv_1 \neq mv_2$  at the two-sided 0.05 level of significance if there is statistical evidence that both VR arms are better than control. Using the same assumptions as above and simulating 10000 trial replicates, then if both VR arms are better than the control arm, we can achieve 71.4% power to detect 5 units in PROMIS score between the two VR arms. This power was derived under the alternative hypothesis  $|m_c - mv_1| = 5$  and  $|mv_1 - mv_2| = 5$ . The actual type I error rate for this conditional test is 0.02.

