### 3.5 Determination of Sample Size

The primary aim is to test the efficacy of immersive VR in improving perceived pain. The trial will be a success if there is statistical evidence that either immersive VR group is better than control (sham) VR.

Preliminary studies showed that the PROMIS pain interference scale has a SD of 10. Assuming that the SD at baseline (SD0) and at 30 days (SD1) are similar and equal to 10 for this population, the variance for the difference in PROMIS from baseline to 30 days after intervention is  $\text{Var}_{\text{diff}} = \text{SD0}^2 + \text{SD1}^2 - 2 \rho \text{SD0} \text{SD1}$ , where  $\rho$  is the correlation coefficient between measurements at baseline and 30 days. A conservative estimate of this variance is achieved when  $\rho = 0$ . Therefore, the estimate  $\text{SD}_{\text{diff}} = (10^2 + 10^2)^{0.5} = 14.14$ . Let  $mc$ ,  $mv1$ , and  $mv2$  be the mean change in PROMIS score from baseline to 30 days for the control, VR1, and VR2 groups, respectively. We estimate power by simulating 10000 trial replicates and testing the null hypothesis that  $H_0: mc = mv1 = mv2$  versus the alternative hypothesis that  $H_1: mc \neq mv1$  or  $mc \neq mv2$ . To maintain the familywise error rate at 0.05, a two-sample t-test is used to compare the control arm to each VR arm and the test is declared statistically significant if the p-value of the two-sided test is less than 0.025. Under the alternative hypothesis that  $|mc - mv1| = |mc - mv2| = 5$ , data from 120 patients in each of the three arms achieve 83% power to detect a clinically meaningful effect 5 units in the PROMIS score. The actual type I error rate is 0.049. For the secondary outcome of comparison between the two VR arms, we test the null hypothesis that  $H_0: mv1 = mv2$  versus the alternative hypothesis that  $H_1: mv1 \neq mv2$  at the two-sided 0.05 level of significance if there is statistical evidence that both VR arms are better than control. Using the same assumptions as above and simulating 10000 trial replicates, then if both VR arms are better than the control arm, we can achieve 71.4% power to detect 5 units in PROMIS score between the two VR arms. This power was derived under the alternative hypothesis  $|mc - mv1| = 5$  and  $|mv1 - mv2| = 5$ . The actual type I error rate for this conditional test is 0.02.

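### The 71.4% power for Skills-based versus Distraction VR is conditional on both arms having beaten sham; the overall power (about 49% on the same sizing inputs) is not reported, and Protocol 9.1 states a different gate

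*SAP*

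**What the plan says.** Protocol 9.2 and SAP 3.5 size the trial on the change in PROMIS Pain Interference to Day 30. Each VR arm is compared with sham by a two-sample t-test, and "the test is declared statistically significant if the p-value of the two-sided test is less than 0.025". With 120 patients per arm and a 5-point difference in both VR arms, the stated power is 83%.

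The two VR arms are then compared with each other "at the two-sided 0.05 level of significance if there is statistical evidence that both VR arms are better than control". Protocol 9.2, SAP 3.5 and SAP 3.5.1 all give the result in the same form: "if both VR arms are better than the control arm, we can achieve 71.4% power to detect 5 units in PROMIS score between the two" arms. They add "This power was derived under the alternative hypothesis" that sham and VR1 differ by 5 and that VR1 and VR2 differ by 5. They put the type I error of what they call a conditional test at 0.02.

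Protocol 9.1 sets another gate for the same comparison: Skills-based versus Distraction is tested if Skills-based versus Sham is significant, with no requirement on Distraction versus Sham. SAP 6.3 promises gatekeeping but does not list the tests, so it does not settle which gate applies.

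Protocol 4.2 makes this comparison a purpose of the design: "The three-arm study design will allow us to determine whether a skills-based VR program" does better than the distraction program.

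**The concern.** The gate is statistical: "if there is statistical evidence that both VR arms are better than control". The power clause drops the reference to evidence and speaks of both arms being better, which reads like an assumption about the truth, the kind that any power figure carries. The following sentence, on the alternative hypothesis, supports that reading. SAP 3.5.1 also prints 71.4% directly after the 83% for the primary endpoint and calls both power, although the 83% is unconditional.

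A reader can therefore take 71.4% as the chance that the trial, as sized, shows a true 5-point difference between the VR programs. If it is not that, the planned comparison is described as stronger than the sizing supports. An outcome of not tested or not significant could then be given too much weight as evidence of no difference.

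**Working it through.** **Inputs, from SAP 3.5 and Protocol 9.2.** n = 120 per arm. For the SD, "Preliminary studies showed that the PROMIS pain interference scale has a SD of 10" at each time point. The correlation between baseline and Day 30 is taken as 0, so the SD of change is √(10² + 10²) = 14.14. Gate tests are at two-sided 0.025 and the VR-versus-VR test at two-sided 0.05. The two 5-point differences are read as mean improvements of 0 (sham), 5 and 10. The other reading of the absolute values, with VR2 equal to sham, contradicts the plan's condition that both VR arms are better; it gives 40.0% conditional power, which does not match.

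**Standard error of a difference.** 14.14 × √(2/120) = 1.826, so 5 points is 5/1.826 = 2.74 standard errors.

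**Single tests (normal approximation; t-test in brackets).**
- 5-point arm versus sham at 0.025: Φ(2.74 − 2.24) = 69.0% (68.5%).
- VR versus VR, 5 points at 0.05, with no gate: Φ(2.74 − 1.96) = 78.2% (77.9%).

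**Simulation of the three-arm trial (400,000 replicates, t-tests).** The plan's own figures come first.

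| Quantity | Means | Simulated | Plan |
|---|---|---|---|
| At least one VR arm beats sham | 0/5/5 | 83.2% | 83% |
| VR versus VR significant, given both gates passed | 0/5/10 | 71.1% | 71.4% |
| Same, when the VR arms are equal | 0/5/5 | 0.0205 | 0.02 |
| Both gates passed | 0/5/10 | 68.4% | not given |
| Both gates passed and VR versus VR significant | 0/5/10 | 48.6% | not given |
| VR versus VR with no gate | 0/5/10 | 77.9% | not given |

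The 10-point arm passes its gate in 99.9% of trials, so the 5-point arm decides whether the gate opens. Overall power = 0.684 × 0.711 = 48.6%; with the plan's own 71.4% it is 0.684 × 0.714 = 48.8%. No test behind this gate can succeed more often than the gate opens, so 71.4% cannot be the overall power. The two steps also pull against each other. A favourable result in the 5-point arm opens the gate but narrows its distance to the 10-point arm. That is why the conditional 71.1% lies below the ungated 77.9%.

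**Gate of Protocol 9.1 (Skills-based versus Sham only, same 0.025 level).**
- Skills-based is the 10-point arm: 77.9%.
- Skills-based is the 5-point arm: 48.6%.

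**Planned model.** Protocol 9.4.2 and SAP 4.6.1 adjust for baseline. With SD 10 at both times, the residual SD after adjustment is 10 × √(1 − ρ²), which is 10 at ρ = 0. With SD 10 in place of 14.14, complete data and the both-arms gate: gate 94.7%, conditional 96.9%, overall 0.947 × 0.969 = 91.7%.

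**Sensitivity, on values that the documents do not give.** For unadjusted change scores, ρ = 0.2, 0.3 and 0.5 give overall power of about 66%, 75% and 92%. With 100 evaluable patients per arm at ρ = 0 it is about 35%.

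**The case against.** The strongest reply is that the plan discloses the condition. The sentence opens with it, and the next figure is attached to a conditional test. This stands in large part. A reader might infer a miscalculation, but the documents do not support that: the figure reproduces within simulation error as the quantity that the wording partly describes. What remains is that the condition can be read in two ways and that neither the gate probability nor the overall power appears anywhere.

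The second reply is that the 49% belongs to a test that the trial will not use for inference. This also stands. A reader might conclude that the trial's real chance of separating the VR programs is a coin flip. The documents do not support that either. Zero correlation with unadjusted change scores is the plan's declared conservative choice. Under the baseline-adjusted model ρ = 0 is the least favourable case, so with complete data the overall power is about 92% or more. An assumed loss of one third, to 80 per arm, brings it to about 70%.

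Third, the 0.02 might be taken as a sign of a mis-stated error rate. It is labelled conditional, it reproduces when both VR arms are 5 points from sham, and at 10 points it is 0.049, still within 0.05. There is no inflation; only the scenario is unlabelled.

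Finally, this is a secondary comparison, and the sample size rests on the primary 83%, which reproduces. That limits the consequence to how the comparison is described and later interpreted.

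**Conclusion.** The concern holds as a misleading power statement. On the plan's sizing inputs, 71.4% is the probability of significance given that both gate tests have succeeded. The overall power for the both-arms gate is about 49%, some 23 points lower (71.4 − 48.6 = 22.8). Under the gate in Protocol 9.1 it is about 78% or 49%, depending on which arm is Skills-based. The printed figure is the unconditional power under neither gate, and it is not comparable with the 83% beside it.

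This rests on 120 evaluable patients per arm, SD of change 14.14, mean changes 0/5/10, gate tests at 0.025 and unadjusted t-tests. It describes the stated sizing calculation and does not forecast the result of the planned model. The conflict between the two gates matters at least as much as the missing number, because no single power can be quoted until it is settled.

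**What to change.** 1. Reconcile the gate for Skills-based versus Distraction between Protocol 9.1 and Protocol 9.2 with SAP 3.5 and 3.5.1, and list the test explicitly in SAP 6.3.
2. State the alternative as mean changes of 0, 5 and 10. If the gate is Skills-based versus Sham alone, also say which VR arm is Skills-based.
3. Report the unconditional power for the chosen gate next to the conditional figure. For the both-arms gate: 49% overall, 71% given that the gate is passed. For the Skills-only gate: 78% or 49% by ordering.
4. Say that these figures are for unadjusted change scores at zero correlation, and that the baseline-adjusted model gives about 92% for the both-arms gate with SD 10, zero correlation and complete data.
5. Optionally, label 0.02 as the conditional error when both VR arms are 5 points from sham.

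The cost is a short rewording and one re-run of the simulation. Enrolment and the primary tests do not change. Choosing one gate settles when the secondary comparison is run, so it should be done before unblinding.

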## 4. STATISTICAL ANALYSES

### 4.1 General Methodology

All statistical analyses will be performed jointly by the Cedars-Sinai Biostatistics Core and the Cedars-Sinai Center for Outcomes Research and Education (CS\_CORE) using SAS® software version 9.3 or higher (SAS Institute, Cary, NC, USA), R pack 4.1.1 (R Foundation for Statistical Computing, Vienna, Austria) or Stata software version 14 or higher (StataCorp LLC, College Station, TX, USA).

Continuous variables will be summarized using descriptive statistics (N, mean, standard deviation, minimum, median, and maximum). Categorical variables will be summarized using the number and percentage of patients in each category. Data will be summarized with respect to patient demographic and baseline characteristics both across the study and by study-arm. The efficacy endpoints, safety assessments, and other outcome results for each treatment group will be summarized descriptively unless otherwise indicated. In addition, statistical model estimates of least squares means, treatment differences, p-values and 95% confidence intervals will also be provided where relevant. The fit of linear models will be assessed using residual plots and/or other diagnostic plots as appropriate. The fit of logistic models will be assessed using Hosmer-Lemeshow goodness-of-fit and/or receiver operating characteristic (ROC) curves as appropriate. All statistical tests will be 2-sided and performed at the 0.05 level of significance unless stated

otherwise. Baseline is defined as the value at the screening week for all parameters, unless specified otherwise.

#### **4.2 Analysis Populations and Patient Disposition**

All efficacy and safety data summaries and analyses will be performed by study arm using an Intent-to-Treat (ITT) population defined as all randomized patients.

The number of patients identified as candidates will be reported, as will the number screened (i.e. consented). The number and percentage of patients randomized, patient population (ITT), and treatment status (completed, discontinued/withdrew) will be summarized both by treatment group and overall. Reasons for discontinuation/withdrawal will be presented.

An exploratory, per protocol (PP) analysis will focus on patients who use the assigned intervention on at least 50% of days during the first 30-day period. Usage meta-data on the headsets will facilitate sample definition in this population.

#### **4.3 Deviations from Protocol**

Protocol deviations/violations impacting participant safety will be reported to National Institute of Arthritis and Musculoskeletal and Skin Diseases (NIAMS) and the Data and Safety Monitoring Board (DSMB) Safety Officer through the Executive Secretary (Navitas Life Sciences) within 48 hours of the investigator becoming aware of the event; all other deviations/violations that do not impact participant safety can be reported as part of the routine DSMB meeting report. The investigator will also report deviations within 2 working days of identification of the protocol deviation to the IRB. All deviations must be addressed in study source documents and reported to NIAMS. Protocol deviations must be sent to the reviewing Institutional Review Board (IRB) per their policies. The site investigator is responsible for knowing and adhering to the reviewing IRB requirements. Protocol deviations will be presented descriptively in results but will not be analyzed.

#### **4.4 Demographic and Baseline Characteristics**

We will summarize demographic and baseline characteristics both by treatment group and overall. Any time-to-event counts will be measured from the day of randomization. Body Mass Index (BMI) will be calculated according to:  $BMI = \text{weight (kg)} / (\text{height (m)})^2$ . Age will be calculated according to:  $Age = (\text{date of event} - \text{birth date} + 1) / 365.25$ . Weekly average opioid dosage will be calculated as a 7-day average of daily maximum milligrams morphine equivalent (MME) as prescribed. Mean activity measures will be calculated as weekly averages (e.g. weekly steps, weekly sleep minutes). Activity classification (i.e. sedentary versus light versus moderate, etc.) will be provided by FitBit and reported as such. Zip code will be matched to median income using census data as an aggregate measure of socio-economic status.

#### **4.5 Treatment Compliance and Dosage**

The cumulative time patients access content and/or engage interactive elements will be summarized descriptively in total and by study-arm. Duration will be calculated by subtracting

the content start time from the content end time. We will summarize treatment compliance in terms of percent of scheduled engagement across all days within patient (i.e. [(Minutes of Content Received) ÷ (Expected Minutes of Content)] \*100) at 30-days and 90-days. The participants will be considered to have completed a module, if they have completed 70% of the module on a given day.

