#### 4.3 JUSTIFICATION FOR DOSE

Prior research has shown that daily use of VR for 10 to 15 minutes is effective in managing pain, plus use as needed for breakthrough flares of pain. The skills-based VR therapy program, EaseVRx, is a standardized 56-day program consisting of scheduled daily virtual experiences. Each VR treatment experience lasts between 2-16 minutes, with an average duration of 6 minutes. To minimize the risk of cybersickness, participants are instructed to complete one VR treatment experience at a time. Given the low-risk nature of VR, they also may repeat experiences such as relaxation, breathing exercises, and games at other times during the day, in response to their pain. After the 56-day program is completed, participants in this arm are instructed to continue daily use, choosing from among the treatment experiences. Participants in the distraction-based VR (EaseVRx-Distraction) and the sham VR also will be instructed to use the VR headset at least once daily, choosing from among the experiences available in their devices.

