#### Skills-Based VR: EaseVRx

EaseVRx was developed by AppliedVR in partnership with pain psychologist [name], Associate Professor of Anesthesiology, Perioperative and Pain Medicine at Stanford University and an NIH- and PCORI-funded investigator in the use of VR for pain management. EaseVRx incorporates the evidence-based principles of CBT, mindful meditation, and physiologic biofeedback therapy using embedded biometric sensors. It combines psychoeducation, pain education, breathing training, relaxation exercises, and executive functioning games to provide a mind-body approach toward living better with chronic pain. The standardized, prescriptive, and reproducible 56-day program delivers a combination of skills training and CBT-related treatments through scheduled daily virtual experiences. The participants are allowed to complete as many sessions as they would like. In addition to the prescribed schedule of content the participant will have access to the full library of content. Each VR experience lasts between 2-16 minutes, with an average duration of 6 minutes. The VR treatment modules are designed to minimize triggers of emotional distress or cybersickness. There are 5 types of modules:

- **Interoceptive:** These modules are designed to help the user understand and perceive what is happening inside the body. They provide a biofeedback-like platform in which the changes in the observed environment reflect a progressively enhanced state of relaxation.
- **Education:** Help the user understand why the VR exercises are relevant to their pain, as well as teaching specific topics often used in pain psychology, including the neurobiology of pain, the role of mood and stress in pain, pain catastrophizing, activity pacing and setting goals. The goal is for the user to create self-management steps and a toolkit of strategies they can use to manage their response to pain.
- **360-degree videos:** High-quality 360 videos with voiceovers, music, and sound effects that are designed to maximize relaxation and engagement of users.
- **Game modules:** Games are designed to maximize distraction and engagement, increasing the cognitive load on patients, and decreasing their perception of pain.

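### SAP 4.5 labels compliance as a share of scheduled engagement but computes uncapped minutes pooled over days, so extra sessions can offset missed days and lift the figure to 100% or more

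*SAP*

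**What the plan says.** SAP 4.5 (Treatment Compliance and Dosage) gives two summaries. The first is time on content: "The cumulative time patients access content and/or engage interactive elements will be summarized descriptively in total and by study-arm". The second is compliance, at 30 and 90 days: "We will summarize treatment compliance in terms of percent of scheduled engagement across all days within patient". Its ratio is "Minutes of Content Received) ÷ (Expected Minutes of Content", times 100. Minutes come from content start and end times. A 70% threshold for counting a module as completed follows the formula but does not enter it. Neither document gives expected minutes as a number or defines them by arm.

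The protocol leaves use above the schedule open. For the skills-based programme (6.1.1): "The participants are allowed to complete as many sessions as they would like", and "In addition to the prescribed schedule of content the participant will have access to the full library of content". On same-day use, 4.3 says participants "they also may repeat experiences such as relaxation, breathing exercises, and games at other times during the day" when in pain. Section 6.1.2 instructs all three arms to use the programme at least daily, and also as needed, for eight weeks.

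The per-protocol set is defined separately in SAP 4.2, by days: "patients who use the assigned intervention on at least 50% of days during the first 30-day period".

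**The concern.** The label and the formula describe different quantities. A share of scheduled engagement should not exceed 100%, and a missed day should lower it for good. The ratio as written does neither. Nothing restricts the numerator to scheduled content, nothing caps it, and pooling over days lets a heavy day pay for an empty one.

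This is the only compliance percentage that the SAP defines. If Day 30 shows no difference, a reader will want to know whether the programmes failed or were not used, and will look here. An arm with many repeats on few days could appear more adherent than an arm used steadily once a day. The same participant could also be fully compliant under SAP 4.5 and excluded from the per-protocol set under SAP 4.2, with no explanation in the plan.

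**Working it through.** The documents state no compliance figure, so there is nothing to reproduce. The check applies the SAP 4.5 formula to simple patterns of use.

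**Inputs**
- Window D = 30 days (SAP 4.5).
- Experience length: 2 to 16 minutes, mean 6 (Protocol 4.3 and 6.1.1, skills-based programme).
- Per-protocol cut: 50% of days, so 15 of 30 (SAP 4.2).
- Assumptions: one scheduled experience a day, and the same mean length for actual and scheduled sessions. Expected minutes would then be 30 × 6 = 180. That total is not in the plan.

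**One participant.** With d days used and s sessions per used day, compliance = 100 × (d × s × length) / (D × length) = 100 × d × s / D. Length cancels, so the result holds from 2 to 16 minutes. Crediting at most one scheduled session a day gives 100 × d / D.

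| Days used | Sessions per used day | As written | Capped by day |
|---|---|---|---|
| 10 | 3 | 100 × 30/30 = 100% | 33.3% |
| 10 | 4 | 100 × 40/30 = 133.3% | 33.3% |
| 8 | 4 | 100 × 32/30 = 106.7% | 26.7% |
| 5 | 4 | 100 × 20/30 = 66.7% | 16.7% |

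Every row fails the 15-day cut. If two experiences a day were scheduled, the 10-day user would need six sessions per used day to reach 100%, not three.

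**Group mean.** Let p be the chance of use on a day and r the mean number of repeats per use-day. Mean compliance = 100 × p × (1 + r). With p = 0.5:
- r = 0: 50%, equal to the capped value
- r = 0.5: 75%
- r = 1: 100%
- r = 1.5: 125%

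The capped value is 50% throughout. The documents give no value for r.

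**Participants below the per-protocol cut.** Take days used as binomial (30, 0.5) and repeats as Poisson with mean d × r. Among those with d ≤ 14, a score of at least 80% needs d + repeats ≥ 24, and 100% needs d + repeats ≥ 30. Exact calculation:

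| r | At least 80% | At least 100% |
|---|---|---|
| 0.5 | about 7.5% | 0.1% |
| 1 | 62.6% | 16% |
| 1.5 | 90.6% | 62% |

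**Day 90.** The denominator is not fixed. Protocol 4.3 has the skills-based arm continue daily use after the 56-day programme; 6.1.2 makes use after eight weeks as needed for everyone. Daily expectation to Day 90 gives 90 × 6 = 540 minutes; the programme alone gives 56 × 6 = 336. A participant who completes exactly the 56-day programme scores 336/540 = 62.2% or 336/336 = 100%. One with 30 used days at 18 minutes (540 minutes) scores 100% or 540/336 = 160.7%; capped on the 540-minute base, 180/540 = 33.3%.

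**The case against.** The best defence is that the formula glosses a phrase about scheduled engagement, so content received could mean scheduled content received. The SAP does not say so. Minutes are defined by start and end times with no split into scheduled and unscheduled content. The reading used here is the plain one, but it is not an explicit definition, and one sentence from the authors could settle that part.

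As-needed use is part of the instructed regimen, so counting it as exposure is reasonable. That supports the cumulative-time summary, which already counts it; it does not make the ratio a share of scheduled engagement.

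SAP 4.1 requires median, SD, minimum and maximum, so a few extreme users would show. This stands in part. If moderate repeats are common, the median moves too, and a score below 100% does not reveal how many days were missed.

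Three stronger readings are tempting and are not supported:
- A reader might infer that the efficacy results are affected. The primary analysis is intention-to-treat, the per-protocol set counts days, and the dose analysis uses minutes of content; none uses this ratio.
- A reader might set the 10 to 15 minutes a day in Protocol 4.3 against the 6-minute average and conclude that 12 days at 15 minutes (180 minutes) gives 100% on the plan's own figures. The 10 to 15 minutes is attributed to prior research, not to this programme. If 15 minutes a day were also expected, 12 days would score 12/30 = 40%.
- A reader might say that the per-protocol rule and the ratio contradict each other. They measure different things, days and minutes. Disagreement between them is possible and needs explaining, but is not in itself an error.

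**Conclusion.** The point holds as a mismatch between label and formula in a descriptive summary. Followed literally, SAP 4.5 can report 100% or more for a participant who missed most scheduled days; 10 of 30 days at three sessions per used day is enough if one experience a day is scheduled and session lengths are equal. How far group figures would shift cannot be derived from the documents: the shift is zero without repeats and grows in proportion to the repeat rate. Express permission for unlimited sessions and the full library is in the skills-based description, but all arms are told to use the programme as needed, so surplus minutes are possible in each. The more basic gap is that expected minutes are undefined by arm and, after Day 56, rest on passages that disagree. The change is worth making before unblinded reporting, because it costs little and the figure bears on how a null result is read.

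**What to change.** In SAP 4.5:
1. Credit at most each day's expected minutes before summing: compliance = 100 × Σ min(minutes received, minutes expected) / Σ minutes expected, over days. For the scheduled programme, credit scheduled modules only, if the headset log allows it. A daily cap on any minutes still credits library content on a day when the scheduled module was skipped.
2. Report the percent of days with any use beside it, by arm, at 30 and 90 days.
3. Keep total minutes, repeats included, in the cumulative-time summary.
4. Define expected minutes by arm and period. Distraction needs particular care, since Protocol 4.3 has participants choose among experiences while 6.1.1 describes a prescribed sequence; Sham is given no scheduled minutes.
5. Have Protocol 4.3 and 6.1.2 reconciled on use after Day 56 before computing the 90-day denominator.

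The cost is SAP wording and a few lines of code. Protocol 8.2.1 already has the headset record time, date and module. The reported figure will be less favourable, and content caught up on a later day will not be credited; the SAP should say so.
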